8. SUMMARY OF STUDY POPULATION DATA

Tables related to the study population will be in Section 14.1 and listings in Section 16.2 of the TLF Shell Document and the CSR.

8.1. Subject Disposition

The total number of subjects enrolled and the total number of subjects in each analysis population will be provided by study part. Among subjects who received any study drug, frequency and percentage of subjects who completed treatment, prematurely discontinued and reasons for premature discontinuation, and reason for end of study will be tabulated.

Separate listings will be provided for subject disposition, inclusion/exclusion eligibility, and analysis population assignment. The disposition listing will include informed consent date, first treatment, last treatment, treatment duration (days), reason for premature discontinuation from study drug treatment, date of study discontinuation, reason for study discontinuation, date of subsequent anti-cancer therapy, and, if applicable, date of death.

8.2. Protocol Deviations

The number of protocol deviations per subject (mean, SD, median, minimum, and maximum), the number and percentage of subjects who presented at least one protocol deviation in each category, and the number and percentage of subjects who discontinued due to protocol violation will be summarized for each study part and overall.

All major and minor protocol deviations will be listed.

8.3. Demographics and Baseline Characteristics

Descriptive statistics will be used to summarize demographics and baseline characteristics for the Safety Population.

Subject demographics and baseline characteristics including age, sex, race, ethnicity, height, weight, and Eastern Cooperative Oncology Group (ECOG) performance status will be summarized by study part.

Medical and surgical history/physical findings will be coded using MedDRA Version 25.1 and summarized by system organ class (SOC)/ preferred term (PT) and study part. Cancer history at screening will be summarized by diagnosis and stage for each study part. Previous anti-cancer therapy, prior cancer surgery, and prior radiation therapy will be summarized by study part and tumor type. Previous anti-cancer therapy will be further categorized as the number and percentage of subjects having any platinum-based antineoplastics, vinca alkaloid therapies, anti-PD-1 agents, or other prior anti-cancer therapies. These summaries will include summary statistics of prior regimens per subject, best overall response, number experiencing peripheral neuropathy (platinum-based antineoplastics only), and number resistant to the therapy (platinum-based antineoplastics and vinca alkaloids only).

Duration on last prior therapy will be calculated as the earliest of Progression Date on prior therapy, Last Date on prior Treatment, or Date of IT-01 Screening less the earliest Treatment Initiation Date of Most Recent Prior Cancer Therapy, converted to months by dividing by 30.4375. A separate tornado plot will present duration on last prior therapy vs. duration on INT230-6 for Cohorts A/B1/EA/EC, EC2/EC3, DEC/DEC2 and FEC.

Listings will be provided for individual subject demographics and baseline medical and surgical history/physical findings, as well as cancer history at screening, previous anti-cancer therapy, prior cancer surgery and prior radiation.

8.4. Dosing and Extent of Exposure

The dose of INT230-6 administered to subjects will be summarized by total dose injected (mL), maximum dose injected into any one tumor (mL), number of tumors injected for each cohort and percent of total tumor burden injected. Drug leakage will also be listed. Subjects receiving study drug per protocol, subjects receiving partial or incomplete drug dose, and reasons for interruption will be summarized. Individual study drug administration records and deviations in administration will be listed, as well as the largest dose into any one tumor.

Pembrolizumab and ipilimumab administration will be summarized in a table and listing and will include total dose administered, dosing delays, reason for dosing delays, number and reasons of subjects permanently discontinuing drug, and number and reasons of infusion interruptions.

8.5. Prior and Concomitant Medications

Prior and concomitant medications will be coded using the World Health Organization Drug Dictionary (WHODD) Version Dec 2016. Prior and concomitant medications will be summarized by preferred term. A listing of prior and concomitant medications by subject will be provided. Non-drug treatments and procedures will be listed.

9. EFFICACY ANALYSES

Due to the method of action of the INT230-6 therapy observed over the course of the study, proper assessment utilizing RECIST or iRECIST was not possible. A response across all lesions using sum of diameters to assess efficacy over time using response criteria was not utilized. Thus, efficacy analyses will largely focus on the response of individual tumors (injected and bystander) as opposed to an overall tumor response, and any overall response will utilize the modified response criteria defined below.

Efficacy analyses will be conducted on the All Treated Population (ATP), the Response Evaluable Population (REP), and the Scan Evaluable Population (SEP). RECIST 1.1 assessments were not collected. Rather injected tumor response and non-injected tumor response utilizing some of the RECIST criteria were evaluated. Sponsor utilized RECIST principles with the injected and non-injected tumor measurements obtained. Efficacy will be determined based on a modified version of RECIST 1.1 criteria. Specifically, complete response (CR) and partial response (PR) will be defined for injected tumors followed per RECIST 1.1 utilizing target lesions. Progressive disease will be determined by clinical or radiological deterioration leading to the subject being taken off-treatment at the discretion of the investigator. Stable disease (SD) is defined as any adequate assessment not considered CR, PR, or progression. The appearance of a new lesion will not necessarily be considered progression and if possible will be assessed. Any post-baseline visit where a target lesion present at baseline was not assessed will result in a Not Evaluable (NE) assessment for that lesion. Data will be presented by treatment and, when indicated, by subgroups.

The primary efficacy parameter is the disease control rate (DCR), defined as the number of subjects obtaining a best overall response of either CR, PR, or SD as described above divided by the total number of subjects in the analysis population. The DCR will be presented with accompanying 95% exact binomial confidence intervals for each study part for the ATP population, REP, SEP, and by subgroup.

At baseline, lesions are classified as measurable or nonmeasurable per either RECIST 1.1 guidelines, depending on the cohort. Baseline measurable lesions are further classified as target (injected) or bystander (non-injected), while non-measurable lesions are classified as non-target (non-target lesions are not eligible for injection). A sum of diameters (SOD) (longest for extranodal lesions and shortest for lymph nodes) will be calculated for all target lesions. Tumor volume (for target tumors with three dimensions) will also be calculated using the modified

ellipsoid method or by longest diameter if specified in an particular protocol amendment. Bystander lesions will be recategorized as target lesions once injected, but target lesions will always remain target lesions.

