14.2.5. Exploratory Biomarker (Immune Function and others) Data Set

All subjects who receive at least one dose of INT230-6 and have at least one measurement for a specific marker will be included in the data set for that marker. All treated subjects with at least one baseline measurement will be included in predictive analyses; treated subjects with baseline measurement and at least one on treatment measurement will be included in pharmacodynamic assessments. Blood biomarker sampling has been eliminated in Amendment 6.

14.2.6. **Retreatment Population**

For cohorts A1, B1, EA, EC, EC2, DEC, those subjects who have completed treatment and have not started any subsequent anti-cancer therapy were eligible for retreatment. Subjects who qualified for re-initiation of treatment were evaluated for safety and efficacy based on availability of data.

14.3. **Statistical Considerations**

Please refer to the Statistical Analysis Plan (SAP).

14.3.1. **Demographics and Baseline Characteristics**

Subject demographics and baseline characteristics including age, sex, race, ethnicity, weight, baseline disease diagnosis, and medical conditions will be summarized by dose level using descriptive statistics.

14.3.2. **Extent of Exposure**

The dose of INT230-6 taken by subjects will be summarized by total dose and number of tumors injected. Additional parameters will be summarized, such a reason for study drug interruption and number of tumors with drug exuded. A by-subject listing of treatment exposure will be generated.

Combination study drugs for cohorts 7 and higher will also be summarized. Details will be provided in the statistical analysis plan.

14.3.3. **Tumor Response.**

The primary efficacy endpoint of disease control rate (DCR), defined as the sum of complete, partial and stable disease responses divided by the total number of subjects in the efficacy population, will be determined per iRECIST criteria for fixed dose and expansion cohorts. DCR will be tabulated by overall and by tumor type. Exploratory analysis will be conducted by cohort, Phase 1 cohorts (monotherapy and PD-1), Phase 2 cohorts (monotherapy, PD-1 and CTLA-4), Phase 1 and 2 cohorts (monotherapy and PD-1), tumor types, study visit, number of INT230-6 doses, number of cycles of INT230-6 (i.e., retreatment), and number of prior lines of therapy. Since iRECIST methods were not implemented at the time of dose escalation, DCR for these cohorts will be analyzed per RECIST v1.1.

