DEC	Dose Escalation, Combination Therapy	PRIMARY	Assess the safety and tolerability of INT230-6 with pembrolizumab	Grade 3, 4, or 5 study drug-related adverse events attributed to the combination and not the underlying disease
		SECONDARY	1) Characterize the overall safety of INT230-6 combined with pembrolizumab 2) Assess the injected tumor response 3) Characterize the pharmacokinetic profile of multiple doses of the three INT230-6 components (CIS, VBL, and SHAO) after single and then multiple IT tumor site injections.	1) Incidence and severity of treatment-emergent adverse events (TEAEs) Clinical laboratory results (hematology, chemistry, urinalysis) ECOG performance status Physical examination, including vital sign measurements ECG results 2) Injected Response Rates 3) C_{\max} , C_{\min} , T_{\max} , AUC_{TAU} , Accumulation index
		EXPLORATORY	1) Characterize tumor response in injected and non-injected sites 2) Evaluate various tumor and anti-tumor immune response biomarkers that may correlate with tumor response 3) Characterize the pharmacodynamics (PD) profile of the INT230-6 plus pembrolizumab in subject blood and in treated and untreated tumors 4) Assess the overall survival in subjects receiving INT230-6 plus pembrolizumab meeting inclusion criteria.	1) Bystander Response Rates, Objective Response Rates, Best Overall Response, Duration of Response 2) Biomarker results 3) PD profile results 4) PFS and OS as defined in Section 9.2 of this document
DEC2	Highest INT230-6 Dose, Combination Therapy	PRIMARY	Preliminary efficacy of INT230-6 combined with pembrolizumab	Disease control rate (CR + PR + SD) of multiple intratumoral doses of INT230-6 combined with pembrolizumab and assessed with criteria based on RECIST or iRECIST
		SECONDARY	1) Characterize the overall safety of INT230-	1) Grade 3 or higher adverse events attributed to the

Cohort	Cohort Description	Number	Objective	Endpoint

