4.4. Study Assessments

Details of scheduled assessments are presented in the study Protocol, with clarifications in Administrative letters 7 and 8. Tumor imaging occurred 12 weeks \pm 10 days after first dose and every 9 weeks \pm 10 days thereafter.

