Individual tumor assessments for target and bystander, non-target, and new lesions will be listed, with location, method of assessment, longest diameter, shortest diameter, depth, volume, and percent change from baseline included for each target and bystander tumor, as well as Total Tumor Burden at Baseline, Cumulative Dose, Percent TTB dosed, and dose category (< 40% versus \geq 40%) per subject. Another listing will be produced for the Abscopal effect of bystander tumors, defined as any bystander tumor with any decrease in tumor size at any point during the study, but before being injected with study drug.

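### SAP 9 counts progression only when the investigator stops treatment, so the DCR is open to upward bias and is not the RECIST/iRECIST rate it is labelled as

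*SAP*

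**What the plan says.** Protocol 14.3.3 says that DCR "will be determined per iRECIST criteria for fixed dose and expansion cohorts", and by RECIST 1.1 for the escalation cohorts. Protocol 18.1.2 makes progression a measured event: unconfirmed progression (iUPD), then confirmed progression (iCPD) if a later scan shows further growth or additional new lesions.

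SAP 9 uses different rules:

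- **Progression:** "Progressive disease will be determined by clinical or radiological deterioration leading to the subject being taken off-treatment at the discretion of the investigator".
- **Stable disease:** "Stable disease (SD) is defined as any adequate assessment not considered CR, PR, or progression". No growth ceiling and no minimum duration is given.
- **Response:** "complete response (CR) and partial response (PR) will be defined for injected tumors followed per RECIST 1.1 utilizing target lesions".
- **New lesions:** "The appearance of a new lesion will not necessarily be considered progression and if possible will be assessed".
- **DCR:** subjects whose best overall response is CR, PR or SD, divided by the analysis population.

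The labels did not follow. The SAP synopsis still lists DCR by iRECIST as a secondary objective. Table 2 gives the DEC2 primary endpoint as a DCR "assessed with criteria based on RECIST or iRECIST" and describes the FEC endpoint in similar terms. SAP 13 lists no changes from the protocol's methods.

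**The concern.** The failure criterion of the main efficacy measure is a treatment decision in an open-label study. If an investigator continues treatment despite growth, enlarging bystander tumors or new lesions, the subject is not a progressor and falls into SD, or into CR/PR if the injected tumors shrank. Either way the subject enters the DCR numerator.

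A reader who takes the RECIST or iRECIST label at face value would compare this figure with rates built on measured progression, and the comparison would not hold. Duration of response inherits the problem, because SAP 9.1 starts its clock at CR, PR or SD and stops it at progression or death.

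**Working it through.** **1. Does the consequence follow from the text?** Take a subject on treatment whose scan shows growth in bystander tumors and a new lesion, with injected tumors unchanged and all assessed.

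| Step | SAP 9 | Protocol 14.3.3 and 18.1 (fixed-dose cohorts) |
|---|---|---|
| Growth or new lesion at this scan | Not PD unless the subject is taken off treatment | iUPD if RECIST 1.1 progression criteria are met |
| Further growth at the next scan | Still not PD if treatment continues | iCPD |
| Best response if no better scan | SD | iCPD |
| In DCR numerator | Yes | No |

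The result follows from the SAP's own sentences and needs no assumption about conduct beyond continued treatment.

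**2. Do the SAP's progression rules agree with each other?**

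- SAP 9 requires deterioration leading to removal from treatment.
- SAP 9.2 dates progression to the end-of-treatment date when the reason is radiographic or clinical deterioration, yet also says that PFS will consider assessments after discontinuation.
- Appendix 1 item 5 accepts deterioration from the end-of-treatment, end-of-maintenance, follow-up and survival forms, and death. It describes these as forms showing that the patient is ending treatment or has died. It excludes a 20% rise in the sum of diameters and new lesions, for PFS.

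So the SAP does not settle whether deterioration first recorded in follow-up is progression. None of the three restores measured progression.

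**3. The plan's own precision figures.** SAP 5 gives 90% intervals at n=16. Two-sided 90% Clopper-Pearson reproduces them: 3/16, 5.31–41.66%; 4/16, 9.03–48.44%; 5/16, 13.21–54.83%. They do not depend on how PD is defined.

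**4. Size per subject.** Each subject wrongly counted as controlled adds 1/n. SAP 4.1.2 gives maximum planned sizes of 15 per FEC tumor type and 44 for DEC2: 1/15 = 6.7 points and 1/44 = 2.3 points. At n=16, 1/16 = 6.25 points.

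**5. Illustration only.** The number affected (m) is not in the documents. Assume n=16 with 5 truly controlled, and let m run from 0 to 5:

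| m scored SD | Reported DCR | 95% exact CI |
|---|---|---|
| 0 | 31.3% | 11.0–58.7% |
| 1 | 37.5% | 15.2–64.6% |
| 2 | 43.8% | 19.8–70.1% |
| 3 | 50.0% | 24.7–75.3% |
| 5 | 62.5% | 35.4–84.8% |

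In general, reported DCR = d + f(1 − d), where d is the true rate and f the share of uncontrolled subjects scored as controlled. With d = 31.25%, f = 10%, 25% and 50% give 38.1%, 48.4% and 65.6%.

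With d = 12.5%, the chance of at least 5/16 counted as controlled is 4.1% at f = 0, 24.1% at f = 10% (rate 21.25%) and 69.3% at f = 25% (rate 34.4%).

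**The case against.** **The change is disclosed and reasoned.** SAP 9 says that proper RECIST or iRECIST assessment was not possible because of how the drug acts, and the SAP revision log refers to this. The rationale for Amendment 5 reports tumor enlargement at the first scan. That supports tolerating early growth, but it is why the protocol chose iRECIST, which waits for confirmation. SAP 9 drops the measurement as well as the wait.

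**Investigators should stop at progression anyway.** Protocol 12.1.6 requires discontinuation for disease progression, and Protocol 5.2.1 treats EC3 subjects until CR, iCPD or two years. This narrows the gap. It does not close it, because Protocol 9.3 allows treatment through apparent progression and the SAP no longer checks the decision against measurements. The detailed rules for DEC2 and FEC sit in supplement sections of which only the contents lists were available, so the gap there cannot be sized.

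**Not every new lesion kept on treatment is an error.** Protocol 18.1.2 allows iSD as best response after iUPD. This stands: only subjects who would reach iCPD, or RECIST 1.1 progression in the escalation cohorts, without an earlier qualifying response or SD are misclassified.

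**A stronger reading that fails.** In EA, EC and EC2 the fifth dose is planned for Day 56, while SAP 4.4 says "Tumor imaging occurred 12 weeks" (plus or minus 10 days) after first dose, that is Day 74 to 94. A reader might infer that completers had no treatment left to stop, so that PD was impossible and disease control 100% by definition. The documents do not support that:

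- Appendix 1 item 5 also takes deterioration from follow-up and survival forms, and death.
- SAP Table 3 and SAP 6.7 show a retreatment option for these cohorts.
- Protocol 8.11 allows dose delays of up to 14 days.
- Protocol 5.3 gives 8-weekly follow-up until Amendment 5, and SAP 6.5 accepts scans from two months.

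**A full iRECIST derivation may not be feasible.** This stands in part. SAP 9 says RECIST 1.1 assessments were not collected. Protocol 12.2.1 defines a target tumor as an injected one, identified at or after baseline, up to 10 of them. Confirmation is due 4 to 8 weeks after iUPD (28–56 days), but scans are every 9 weeks plus or minus 10 days (53–73 days), so the two overlap only on days 53–56. A measurement-based DCR is therefore not shown to be fit as the sole primary figure.

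**The stakes are limited.** The study's overall primary objective is safety, and DCR is descriptive, single-arm and without a success threshold. That is fair, but Table 2 still makes DCR primary for DEC2 and FEC.

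**Conclusion.** The point holds as a matter of definition. Under SAP 9 a subject with measured growth or new lesions who stays on treatment counts as disease control, so the reported DCR is open to upward bias and is not the rate that Protocol 14.3.3 specifies. The labels in the synopsis and Table 2, and the empty SAP 13, misdescribe it. SAP 9 and 9.2 also need reconciling with Appendix 1 item 5.

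The size is unknown. The per-subject figures are arithmetic on recruitment ceilings, not estimates of bias; DEC and DEC2 are pooled for analysis (SAP 7.1), and only 110 subjects were enrolled in all. The n=16 tables rest on assumed values of m, d and f.

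**What to change.** 1. **Reconcile SAP 9 and 9.2 with Appendix 1 item 5.** Radiographic or clinical deterioration recorded on any form, including follow-up, should count as PD for DCR whether or not treatment was continuing.
2. **Add a measurement-based DCR beside the investigator-based one.** SAP 9.1 already says that "Individual tumor assessments for target and bystander, non-target, and new lesions will be listed", and Protocol 18.1.5 asks for every baseline lesion to be measured at each evaluation. Use RECIST 1.1 progression thresholds for the escalation cohorts and iUPD/iCPD for EC3, DEC2 and FEC. State the lesion set, use the next available scan for confirmation, and show subjects with missing lesions as not evaluable. Because EC2/EC3 and DEC/DEC2 are pooled, show which criterion applies to each cohort.
3. **Correct the record.** Label the investigator-based DCR as not RECIST/iRECIST in Table 2 and the synopsis, and enter the change and its reason in SAP 13.

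The cost is SAP wording and extra programming on measurements the plan already intends to list. The downside is some not-evaluable subjects and probably a lower DCR.

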12.2.1. Primary Efficacy Parameter

The primary efficacy parameter is disease control rate (CR + PR + SD), as assessed using iRECIST (Appendix 1 Section 18.1). Per iRECIST criteria, up to 5 target tumors are identified at baseline and followed. In this study, a target tumor is a single injected tumor identified at baseline or post baseline, and up to 10 target tumors will be followed. Please refer to the Statistical Analysis Plan for tumor definitions. Subject to PI discretion, cohorts EC3, DEC2, FEC and potentially GEC may have any number of tumors injected during a given session. Record as many tumor measurements in the CRF as possible.

Evaluation of individual injected tumors will take place at every visit, with overall response (Complete, Partial, Stable, Progressive, Not Evaluable) adjudicated for each. ITR calculation could include original target tumors, bystander tumors that become injected, and new measurable lesions that are injected.

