18.1.4. Response and Stable Disease Duration (RECIST 1.1 and iRECIST)

Response duration will be measured from the time measurement criteria for CR/PR or iCR/iPR (whichever is first recorded) are first met until the first date that recurrent or progressive disease is objectively documented, taking as reference the smallest measurements recorded on study (including baseline).

Stable disease duration will be measured from the time of start of treatment until the criteria for progression are met, taking as reference the smallest sum on study (including baseline).

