Ultrasound. Ultrasound is not useful in assessment of lesion size and should not be used as a method of measurement. If new lesions are identified by ultrasound in the course of the study, confirmation by CT is advised.

Endoscopy, Laparoscopy. The utilization of these techniques for objective tumor evaluation is not advised. However, they can be useful to confirm complete pathological response when biopsies are obtained or to determine relapse in trials where recurrence following complete response or surgical resection is an endpoint.

Tumor Markers. Tumor markers alone cannot be used to assess objective tumor response. If markers are initially above the upper normal limit, however, they must normalize for a patient to be considered in complete response.

Cytology, Histology. These techniques can be used to differentiate between PR and CR in rare cases if required by protocol (for example, residual lesions in tumor types such as germ cell tumors, where known residual benign tumors can remain). When effusions are known to be a potential adverse effect of treatment (e.g. with certain taxane compounds or angiogenesis inhibitors), the cytological confirmation of the neoplastic origin of any effusion that appears or worsens during treatment when the measurable tumor has met criteria for response or stable disease is advised to differentiate between response or stable disease and progressive disease.

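### SAP 9 credits stable disease with no minimum interval and no list of qualifying assessments, so DCR cannot be read as disease control through the first scheduled response scan

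*SAP*

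**What the plan says.** SAP 9 (Efficacy Analyses) sets the rules for the primary efficacy parameter.

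- Stable disease: "Stable disease (SD) is defined as any adequate assessment not considered CR, PR, or progression". The term adequate is not defined.
- DCR: "defined as the number of subjects obtaining a best overall response of either CR, PR, or SD as described above", divided by the number in the analysis population.
- Progression: "Progressive disease will be determined by clinical or radiological deterioration leading to the subject being taken off-treatment at the discretion of the investigator". Also: "The appearance of a new lesion will not necessarily be considered progression".

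No minimum SD interval appears in SAP 9, SAP Appendix 1 or Protocol Appendix 1 (18.1). Protocol 18.1.4 says how long SD lasts, but not how long it must last to count: "Stable disease duration will be measured from the time of start of treatment until the criteria for progression are met".

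On timing, Protocol 12.2.1 says "Evaluation of individual injected tumors will take place at every visit", with a response category, Stable among them, assigned to each tumor. Protocol Table 12 schedules US/CT of the injected tumor on each dosing day of the two-weekly monotherapy cohorts. Protocol 12.1.3.2 lists response assessment among the procedures for Cycles/Doses 2 to 5. Scheduled response imaging comes later. SAP 4.4 states "Tumor imaging occurred 12 weeks" after first dose, with a 10-day window, and footnote 10 to Protocol Tables 11 to 13 agrees. For cohorts A1 and B1, Protocol 12.1.3.1 gives a response assessment every two months.

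**The concern.** A best overall response needs only one qualifying time point. With no minimum interval, a single uneventful look fixes the subject as disease controlled, whatever follows. Progression does little to limit this, because it requires removal from treatment and a new lesion need not count.

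DCR is the primary efficacy parameter in SAP 9 and the primary endpoint of DEC2 and FEC in SAP Table 2. The trial is single-arm and states no reference DCR, so the meaning of the result rests on the endpoint definition. If early looks qualify, DCR partly measures staying on treatment until that look. If only scheduled scans qualify, it measures something closer to control at about 12 weeks. The SAP does not say which, so two programmers could derive different DCRs from the same data.

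**Working it through.** **The plan's own figures.** The only design figures are the 90% intervals for 16 subjects (Protocol 14.1, SAP 5). The exact Clopper-Pearson limits are the 0.05 quantile of Beta(x, n−x+1) and the 0.95 quantile of Beta(x+1, n−x). With n = 16 they give 5.31–41.66% for x = 3, 9.03–48.44% for x = 4 and 13.21–54.83% for x = 5, which match. They do not depend on how SD is defined. The plan gives no figure that does.

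**Applying the rule as written to three hypothetical subjects.**

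1. Unremarkable injected-tumor image on Day 14, removed for deterioration on Day 40. If the image qualifies, best response is SD. The subject is controlled in the All Treated and Response Evaluable populations and absent from the Scan Evaluable Population, which requires a scan at two months or later.
2. Same Day 14 image, scanned on Day 80 and removed for deterioration that day. The subject now enters the Scan Evaluable Population, and best response is still the Day 14 SD: controlled.
3. Deteriorates on Day 10 before any assessment. No SD exists, so the subject is not controlled in the All Treated Population.

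Subjects 1 and 2 are the problem. The third is handled correctly already.

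**Size, as an illustration.** The documents give no deterioration rate, so these inputs are assumed: exponential time to deterioration with a median of 2, 3 or 4 months, no responders, and every subject assessed at the stated day. The earliest in-window first scan is 12 × 7 − 10 = 74 days after first dose. With one month = 30.4375 days, the share free of deterioration at day t is S(t) = 0.5^(t / median).

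| Median | In days | S(14) | S(74) | Gap (points) |
|---|---|---|---|---|
| 2 months | 60.875 | 0.853 | 0.431 | 42.2 |
| 3 months | 91.3125 | 0.899 | 0.570 | 32.9 |
| 4 months | 121.75 | 0.923 | 0.656 | 26.7 |

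Cohorts A1 and B1 are dosed every 28 days, so they have no Day 14 dosing image. Comparing a Day 28 look with a two-month assessment (about Day 56):

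| Median | S(28) | S(56) | Gap (points) |
|---|---|---|---|
| 2 months | 0.727 | 0.529 | 19.8 |
| 3 months | 0.809 | 0.654 | 15.5 |
| 4 months | 0.853 | 0.727 | 12.6 |

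If only scheduled scans feed best overall response, the effective minimum is already about Day 74 (about Day 56 in A1/B1), and most of these gaps do not arise.

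**The case against.** The strongest reply is that early looks were never meant to count. Footnote 8 to Protocol Tables 11 to 13 says the dosing-visit US/CT measurements guide the needle. Footnote 10 has response assessed on CT/MRI or PET/CT, first at 12 weeks. Protocol 18.1.5 states "Ultrasound is not useful in assessment of lesion size and should not be used as a method of measurement". Protocol 12.2.2 uses the same every-visit wording for bystander tumors, which the dosing-visit row does not image, so it may mean every tumor-assessment visit. Under SAP 9 an unassessed target lesion is not evaluable, so an image of only some targets may not be adequate.

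This stands to a point: the documents permit a Day 14 SD but do not establish that one would be used. It does not close the gap, because SAP 9 makes none of these a condition for SD, and CT at a dosing visit is not barred. SAP 6.4 accepts any on-treatment tumor evaluation, while SAP 6.5 asks for a scan at two months or later. That contrast suggests the SAP recognises evaluations that are earlier or are not scans.

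A second reply is that duration is visible elsewhere. SAP 9.1 starts duration of response at the first CR, PR or SD and summarizes it by Kaplan-Meier; SAP 9.2 lists PFS. Both help a careful reader, but neither changes who counts in DCR.

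Third, the schedules and imaging sections for DEC2 and FEC appear only in the supplements' contents lists in the text available here. How the point applies to those cohorts cannot be checked.

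**Conclusion.** The definition is incomplete. SD has no minimum interval, the qualifying assessments are not named, and one SD is enough for DCR even if deterioration follows. DCR as written therefore cannot be read as control through the first scheduled response scan, and the Scan Evaluable analysis does not repair it.

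The 27 to 42 points (13 to 20 in A1/B1) are conditional. They rest on assumed medians, an exponential curve, and every subject having an early assessment that qualifies. They show what the wording could allow, not an estimate of bias in this trial.

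A reader might infer that DCR says nothing about disease control, or that an inactive drug is bound to score highly because Day 14 images count. The documents do not support either. Failures before any assessment already count against DCR in the All Treated Population, and whether early images qualify is unsettled. Nor would a minimum interval make DCR evidence of activity: at Day 74 the same no-effect illustration still gives 43% to 66%. That is a limit of any single-arm DCR that includes SD.

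**What to change.** In SAP 9, count SD toward DCR only when both conditions hold:

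- A scheduled CT/MRI or PET/CT response assessment (chest/abdomen/pelvis plus known disease sites) is made at or after the cohort's first scheduled response scan, less its window. That is about two months for A1/B1, 74 days after first dose where the 12-week schedule applies, and as set in the supplements for DEC2 and FEC. State it in days since first dose: the protocol calls the first dose Day 0, while SAP 7.1 adds one, making this Study Day 75.
- Neither progression as the SAP defines it (removal from treatment for clinical or radiological deterioration) nor death has occurred on or before that assessment.

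State that dosing-visit needle-guidance images and ultrasound do not qualify. Subjects without CR or PR who deteriorate, die or leave before that point stay in the All Treated denominator as not controlled.

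The cost is SAP wording, a small amount of derivation work with a cohort-specific cutoff, and a lower reported DCR. SAP 2 requires the plan to be final before database lock, so the rule should be settled before then.
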